### 3.1.3 Exploratory objectives.

Exploratory objectives are not part of primary or secondary outcomes and the exact analyses methods are not detailed here. To assess if water supplementation during one year leads to alterations in

- Reported diet intake. This objective is exploratory but reported diet intake regarding alterations in e.g. sugar sweetened beverages and adherence to Nordic Diet Recommendations 2023 can have an important mediating effect on both primary and secondary endpoints. Reported diet intake was collected using a software from the Swedish National Food Agency, and they declined continuation of the license from last quarter of 2023. Thus, we have missing data in subjects who had not completed their V8 before that time point. We estimate approximately 30% of missing data for the diet analyses (i.e. do not have complete data at baseline and V8). We plan exploratory analyses to test if water vs control therapy leads to differences in change of intake of main nutrients (protein, carbohydrates and fat energy intake relative to total caloric intake) over the 12-month period. These analyses will be performed using t-test (treatment group differences between delta values).

The first step of statistical analysis will be to produce descriptive statistics for some baseline parameters on reduced population (those with baseline and at least one post-baseline value), by intervention group and compare those results with the ITT population. Variables taken into account are those potentially impacting the primary outcome (fasting glycemia) and could be the sex (Male/Female), the age at enrolment (Years), the BMI at baseline ( $\text{kg}/\text{m}^2$ ), the total energy intake at baseline ( $\text{kcal}/\text{day}$ ) from three non-consecutive days of 24-h dietary recall, if possible, 2-h plasma glucose level from OGTT at baseline ( $\text{mmol}/\text{L}$ ) and the waist circumference (cm). If we notice a clinical imbalance between study groups (control and intervention groups in the reduced population vs. the ITT population) for those variables, they could be considered as potential covariates in sensitivity models for primary and secondary analysis. Three other variables could also be considered for the sensitivity analysis: newly diagnosed with T2DM (Yes/No), management of T2DM (initiation of intensive lifestyle therapy if possible and initiation of hypoglycemic drug therapy) and drug therapy impacting the fasting glycemia (Yes/No).

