### 3.3 Sample size

The primary outcome parameter is the difference between active (=extra water) and control treatment in the change of fasting plasma glucose between baseline and 12 months. We use prior effect estimates from the largest RCT for diabetes prevention study in Europe, i.e. the Finnish Diabetes Prevention Study (FDPS) (New Engl J Med 2001;344:1343-50), which compared individual life style counselling (active treatment) with general oral and written life-style advice (control treatment) in relation to risk of new onset type 2 diabetes and change of plasma glucose concentration and found a 58% decreased relative risk of diabetes. After 12 months, the fasting glucose in the active treatment group was reduced by  $4 \pm 12$  mg/dL vs a  $1 \pm 12$  mg/dL increase in the control group with the mean difference of 5 mg/dL of the 12-month change of fasting glucose being highly significant ( $P < 0.001$ ).

To obtain sufficient statistical power to detect a clinically significant effect size, we base the power calculation on an effect of water vs control that is at least 50% of what is considered an epoch changing effect of lifestyle i.e., the difference observed in the FDPS, while assuming the standard deviation for the change ( $s = 0.67$  mmol/L) as observed in FDPS. To be able to detect  $\geq 50\%$  of that effect (a difference of 2.5 mg/dL = 0.14 mmol/L between treatments in 12-month change) we need 319 evaluable subjects in both the active and control treatment group at a power of 80% and a 2-tailed significance level of =0.05, a total of 638 evaluable subjects. As the glucose measurement in the study used a more recent and exact method, the standard deviation of the change of glucose was recalculated by the DSMB in October 2022 from the first completed 357 study participants ( $s = 0.58$  mmol/L). With this smaller standard deviation, the power (with all other assumptions unchanged) was 270 evaluable subjects per group, i.e.  $n=540$  evaluable subjects in total. When also taking into account a dysbalance (with slightly higher drop-out rate in subjects in the intervention group), a total of 544 evaluable subjects were estimated to be needed for 80% power.

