**OR Delta 24h UVol (Baseline vs. 3 months, 6 months, 9 months and 12 months):**

- Control Group: Those with an increase in delta 24h UVol not greater than 500 mL from baseline.
- Intervention group: Those with an increase in delta 24h UVol of at least 1000 mL from baseline.

Furthermore, all individuals attending a clinic study visit (V3, V6 or V8) in a non-fasted state will be excluded from the per protocol analyses. Some other protocol deviations let to exclude patients are detailed in Section 5.1.2

Missing data

Missing data on outcomes (i.e. change of fasting glucose and the secondary cardiometabolic measures) will not be imputed, so subjects with missing data on outcome parameters will not be included in analysis of the respective outcome. For each of the outcomes, the maximum number of subjects will be included (e.g. if there are n=544 evaluable subjects for fasting glucose change, all of these will be included even if there are less evaluable subjects for any other cardiometabolic outcome parameter).

Given the randomized nature of the study, we will not perform any adjustments (which in turn can be affected by missing data on the covariates adjusted for) with three exceptions: (1) As detailed in “statistics” we will include adjustment for the baseline value of the outcome parameter in question (e.g. the change of glucose outcome will be adjusted for the baseline value of glucose). The motif of this adjustment is to minimize bias related to regression towards the mean. (2) As the randomization is stratified by sex, this covariate will be included in all outcome analyses. (3) If clinically significant/meaningful treatment group differences appear in baseline values of age, BMI or diabetes status in any outcome analysis, we will add a sensitivity outcome analysis in which we adjust for such baseline differences. Any missing values for these covariates will be imputed to obtain the same number of evaluable subjects in non-adjusted and adjusted analyses. The technique we propose is Multiple Imputation by Chained Equations (MICE) with subsequent application of Rubin’s rule to combine results from different imputations. We will base the analyses on 20-30 imputed data sets. For this analysis we will use SAS PROC MI in combination with PROC MIXED/PROC GLM and PROC MIANALYZE.

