### 5.7.2 Analysis of secondary outcome parameters

New-onset diabetes is defined as 2 consecutive fasting plasma glucose values  $\geq 7.0$  mmol/L or 2-hour post OGTT value of  $\geq 11.0$  mmol/L after the baseline exam (V3). In addition, new onset diabetes is considered present if diagnosed by a physician outside of the current study, as assessed in the questionnaire (answering yes on having had a physician diagnosis of diabetes or having been prescribed

medication for diabetes) after the baseline exam (V3). All individuals with a diagnosis of diabetes at or before the baseline exam (V3) will be excluded in the analysis of incidence of diabetes.

The difference in diabetes incidence between the intervention and control group will be analyzed using logistic regression with diabetes incidence as the binary outcome and treatment arm as exposure variable and reported as the odds ratio (OR) including 95 % CI for diabetes incidence in intervention vs control. As the randomization should lead to no difference in diabetes risk factors, the main analysis will only be adjusted for sex (as the randomization is stratified by sex, this covariate will be included in all outcome analyses), but we will also add a sensitivity analysis to adjust for key diabetes risk factors at baseline (fasting glucose, diabetes status, BMI, age), if there is a clinically significant difference in these factors between treatment groups despite the randomization.

Cardiometabolic risk factors will be analyzed using the same method as for the primary outcome, but with baseline value for the actual factor as a covariate instead of baseline value of fasting plasma glucose.

In addition, to assess the possible association between change in fasting plasma glucose levels, copeptin, other cardiometabolic risk factors, other blood laboratory parameters and urine laboratory parameters, we propose to analyze correlation(s) between delta value of outcome parameters and delta value of the efficacy parameters (e.g. urine volume, urine osmolality and plasma copeptin) with Pearson or Spearman correlation analyses.

- Outcome parameters are fasting plasma glucose and all secondary continuous outcome parameters listed in section 5.7.1 above.

We emphasize that in these correlation analyses, copeptin will be regarded both as an outcome parameter and as an efficacy parameter.

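### The planned correlations of change with change (SAP 5.7.2) take no account of treatment arm, so they mix the between-arm contrast with any within-arm relationship

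*SAP*

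**What the plan says.** After the treatment comparisons, SAP 5.7.2 adds a further analysis "to assess the possible association between change in fasting plasma glucose levels, copeptin", the other risk factors and the laboratory parameters. The outcomes are fasting glucose and every continuous secondary outcome in 5.7.1. For this, "we propose to analyze correlation(s) between delta value of outcome parameters and delta value of the efficacy parameters", specified as "e.g. urine volume, urine osmolality and plasma copeptin) with Pearson or Spearman correlation analyses". Copeptin has two roles: "copeptin will be regarded both as an outcome parameter and as an efficacy parameter".

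The text does not say whether the arms are pooled, analysed separately or adjusted for, and it does not name the analysis set. The other analyses in 5.7.2 are explicit on this. The diabetes model has treatment arm as its exposure, and the risk-factor models follow the primary mixed model, with treatment, sex and baseline.

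The general rule under Missing data in SAP 4.1 is that "we will not perform any adjustments (which in turn can be affected by missing data on the covariates adjusted for) with three exceptions": the baseline value of the outcome, sex, and (as a sensitivity analysis) age, BMI or diabetes status if they differ between groups. None of these brings arm into the correlations.

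**The concern.** The intervention exists to raise urine volume and to lower urine osmolality and copeptin. The per-protocol limits in SAP 4.1 show the separation sought: a urine volume rise of at least 1000 mL under water against no more than 500 mL in controls, or an osmolality fall of at least 50% against no more than 25%.

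If water also moves an outcome by any route, the two arm means alone tilt a pooled scatter of outcome change against marker change. SAP 3.1.3 itself names a route other than vasopressin: altered diet, including sugar-sweetened beverages, which "can have an important mediating effect on both primary and secondary endpoints".

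A pooled coefficient therefore combines two things: the treatment contrast, already estimated by the mixed model, and the relationship between individuals treated alike. Only the second says whether people whose copeptin fell more also had a larger fall in glucose. The protocol's hypothesis is that water lowers glucose because it suppresses vasopressin. In a positive trial, a significant copeptin–glucose correlation could easily be taken as support for that hypothesis when it partly restates the main result. SAP 5.7.1 lists 22 continuous outcomes and 5.7.2 names three markers, so the issue recurs across many pairs.

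**Working it through.** **Inputs from the documents.** SAP 3.3: "a difference of 2.5 mg/dL = 0.14 mmol/L between treatments in 12-month change"; re-estimated SD of the change 0.58 mmol/L; "a power of 80% and a 2-tailed significance level of =0.05"; 544 evaluable subjects. SAP 5.1.3: 46% intervention, 54% control.

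**Assumed input.** The between-arm shift in marker change, dx, in within-arm SD units. The documents give no value; 0.5 to 2 is shown.

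**Reproducing the plan's figure.** Per group at 1:1, n = 2 × (1.960 + 0.842)² × 0.58² / 0.14² = 2 × 7.849 × 0.3364 / 0.0196 = 269.4, so 270, as the SAP states. At 46:54 the same formula gives 293 + 250 = 543 against 544 stated, and power at 544 is 80.1%. The sample size and effect size used below are therefore the plan's own.

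**Induced correlation.** Let p = 0.46, so p(1−p) = 0.2484, and let dy be the outcome shift in SD units. With zero within-arm correlation, the pooled correlation is

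r = p(1−p)·dx·dy / √[(1 + p(1−p)·dx²)(1 + p(1−p)·dy²)].

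At the design effect dy = 0.14/0.58 = 0.241. For dx = 1: r = 0.2484 × 0.241 / √(1.2484 × 1.0145) = 0.0600/1.1254 = 0.053. For dx = 2: r = 0.1199 / √(1.9936 × 1.0145) = 0.1199/1.4221 = 0.084. The two-sided 5% critical value of |r| at n = 544 is 0.084, so about half of trials would be significant at dx = 2.

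**Simulation.** 4,000 trials per row, 250 and 294 subjects, no within-arm relationship. The last three columns are the percentage of trials with P<0.05.

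| Outcome shift | dx | Induced r | Pearson, pooled | Spearman, pooled | Adjusted for arm |
|---|---|---|---|---|---|
| 0.14/0.58 (design) | 0.5 | 0.029 | 9.8 | 9.7 | 4.9 |
| | 1 | 0.053 | 24.1 | 23.0 | 4.8 |
| | 1.5 | 0.072 | 39.3 | 40.1 | 5.2 |
| | 2 | 0.084 | 49.6 | 50.6 | 5.0 |
| 0.28/0.58 (twice design) | 1 | 0.104 | 68.0 | 67.1 | 4.9 |
| | 2 | 0.165 | 97.5 | 97.7 | 5.4 |
| None | 1 | 0 | 4.6 | 4.9 | 4.6 |
| | 2 | 0 | 5.5 | 5.3 | 5.0 |

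The artefact needs water to move both variables. It disappears when the outcome is not moved, and adjustment for arm removes it in every row.

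**The case against.** Several points on the other side have force.

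- **Pooling is inferred from silence.** The SAP never says the arms are pooled, and running the correlations by arm would not contradict it. Likewise, 5.7.2 says sex will be in all outcome analyses, and whether that covers the correlations is unclear. This stands as a limit on the wording. Still, a plain Pearson or Spearman coefficient takes no covariates, and nothing in the plan supplies an arm term.
- **The SAP speaks only of a possible association.** It makes no claim about mechanism or mediation. The 23% to 50% is not type I error for the test as written, because the pooled correlation is truly non-zero in those scenarios. It is misleading only as an answer about individual-level tracking. This stands, and it is why the interpretation needs to be written down.
- **The induced correlation is small.** At the design effect r stays below 0.1 and at least half of trials would show nothing significant. A reader might infer that every outcome moved by water is bound to show a significant correlation. The figures do not support that: the effect holds in expectation and approaches certainty only with larger effects and strong separation.
- **Adjusting for arm is not a test of mechanism.** It leaves within-arm variation, which is observational and diluted by measurement error. If copeptin fully mediated an effect of design size and the observed marker change had reliability 0.5 (an assumption), the arm-adjusted correlation would be significant in only 81%, 46% and 29% of trials at marker shifts of 1, 1.5 and 2 observed SD. With perfect reliability the figures are 100%, 97% and 80%. A null adjusted coefficient would therefore not refute the pathway. This stands in full and shapes the remedy.

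Two further readings are tempting but not supported. Copeptin's double role could be taken to mean that it is correlated with itself. The natural reading is that it serves as an outcome against the urine markers and as a marker against the other outcomes. Nor are these correlations the sole link between hydration and glucose in the plan, since the per-protocol analyses and the copeptin subgroups also bear on it.

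**Conclusion.** The concern holds as a point about specification and interpretation. Read plainly, the planned correlations pool the arms and partly repeat the randomised contrast. At the design effect on glucose, with 544 subjects split 46:54 and no within-arm relationship, the induced correlation is about 0.05 to 0.08 for assumed marker shifts of 1 to 2 SD. It is significant in about 23% to 50% of trials, against about 5% with adjustment for arm. At a shift of 0.5 SD the rate is about 10%. These rates depend on the assumed marker shift; the direction of the problem does not, provided water moves both variables.

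The analysis is ancillary. The primary and secondary treatment comparisons, the sample size and the conclusions drawn from them are untouched. The matter goes beyond missing detail, because a better analysis is available from data already scheduled for collection.

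**What to change.** In SAP 5.7.2:

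1. Specify partial (Pearson or Spearman) correlations adjusted for arm, or regressions of outcome change on marker change with arm, sex and the baseline values of both variables.
2. Report the coefficient within each arm alongside the adjusted one.
3. If a pooled correlation is also shown, label it as including the between-arm contrast, and do not read it alone as evidence that individual marker change tracks outcome change.
4. State that the arm-adjusted coefficient is itself observational, and that it neither proves nor rules out mediation by vasopressin.

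The cost is a few sentences, a few lines of code, a little more output and a few degrees of freedom out of about 540. No new data are needed.

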## Analysis of safety

### 5.7.3 Adverse events

See section “*Definition and registration of adverse events*” of the protocol. AE and SAE will be reported for all subjects who attended baseline exam and commenced study treatment (i.e. attended V3). AE and SAE will be reported as a diagnosis code (<http://icd.internetmedicin.se/>) associated with the AE/SAE, and the incidence of AE and SAE will be compared between treatment groups (intervention vs control).

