The signature of the study informed consent form marks the inclusion of the subject in the study. This signature will be obtained after having fully briefed the subject about the study and answered all of his/her questions about the study.

Safety reporting: The following variables will be followed at each visit in order to assess safety measurements: serum creatine, serum osmolality and serum sodium to control for water balance problem.

Definition and registration of adverse events: An adverse event (AE) is defined as any untoward medical occurrence in a participant who is administered an investigational product. The medical occurrence does not necessarily have to have a causal relationship with the treatment. An AE can therefore be any unfavorable and unintended sign (including an abnormal laboratory finding, symptom, or disease temporally associated with the use of an investigational product, whether or not related to the investigational product.

AEs are defined as either a laboratory measurement outside the reference range (i.e. a value outside the reference values) or signs or symptoms reported by the participants during regular follow-up contacts (telephone calls and visits). During these contacts the participants will be asked if it has occurred any new or worsened health problems or any medical treatment or hospitalization since the last contact. AEs are documented in the eCRF. We will specifically ask about pregnancy, lactation and new use or change of medication.

AEs are categorized as serious (SAEs) if they result in death, illness requiring hospitalization, events deemed life-threatening, or if they result in persistent or significant disability/incapacity, or in a congenital anomaly/birth defect or medically important condition. SAEs will be reported to the sponsor within 24 hours, as well as recorded in the eCRF (V-CMS). The sponsor will report all SAEs to Danone Research within 3 days. The Adverse Event Form will be sent by email/fax to the following contact:

Position(*)	Name	Cell Phone	Email
Clinical Operations Leader	[name]	[contact]	[contact]
Hydration Physiology and Metabolism Junior Scientist	[name]	[contact]	[contact]

Registration of AEs will start with the 1st telephone contact (which is the first follow up after start of treatment). The registration of AEs ends at the 12-month visit (end of treatment).

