#### Intention to treat

The “Intention-to-Treat” population: all randomized study subjects with at least two during study fasting plasma glucose measurements will be analyzed in intention to treat analysis (i.e. regardless of any protocol deviations). This analysis set includes the evaluation of primary and secondary outcomes as well as adverse events (AE) and serious adverse events (SAE) between intervention and control group.

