### 5.1.3 Populations

We expect a final study sample for intention to treat analysis of at least n=544 evaluable study subjects who have completed the protocol (i.e. with at least 2 fasting glucose measurements, meaning at V3 and at either V6 or V8 or at both V6 and V8). We expect a dysbalance in the final study sample (46% intervention vs 54% control therapy) due to dysbalance in the drop-out rate between intervention and control groups.

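### AE and SAE incidence is to be compared by arm without regard to time observed, although more drop-out is expected under water; the crude comparison can understate water-arm events

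*SAP*

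**What the plan says.** **Safety comparison.** SAP 5.7.3 states that "AE and SAE will be reported for all subjects who attended baseline exam and commenced study treatment (i.e. attended V3", and that "the incidence of AE and SAE will be compared between treatment groups (intervention vs control". It does not say whether incidence means subjects, events or person-time, and it names no method. Section 6.1 covers only primary and secondary outcomes.

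**A second safety population.** SAP 4.1 defines the intention-to-treat set as "all randomized study subjects with at least two during study fasting plasma glucose measurements" and adds: "This analysis set includes the evaluation of primary and secondary outcomes as well as adverse events (AE) and serious adverse events (SAE". That is a smaller set than all V3 attenders.

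**How AEs are found.** Under the protocol's AE definition, an AE is an out-of-range laboratory value or a sign or symptom reported at a follow-up contact. The protocol's study procedures have every participant asked, at each visit after baseline and each call, about the period since the last contact. On timing: "Registration of AEs will start with the 1st telephone contact (which is the first follow up after start of treatment", and "The registration of AEs ends at the 12-month visit (end of treatment". No contact at withdrawal is described.

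**Expected drop-out.** SAP 5.1.3 expects 46% intervention and 54% control in the final sample, "due to dysbalance in the drop-out rate between intervention and control groups". Section 3.3 calls the intervention drop-out rate slightly higher. Section 6.3 describes drop-out from V2 to V3 as balanced and later drop-out as slightly unbalanced.

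**The concern.** A subject who leaves stops generating recorded AEs but stays in the V3 denominator. If more water subjects leave, that arm is observed for less time, and a simple proportion with an event falls for that reason alone. The effect is most direct for laboratory AEs. Sodium, osmolality and creatinine are measured after baseline at 3 weeks and 3, 6, 9 and 12 months, so a subject gone before 6 months has at most two of five chances to show an abnormal value. These are the protocol's own measures of water-balance problems. At stake is whether the safety table gives a fair picture of the intervention.

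The two populations make this worse. Under the section 4.1 definition every drop-out, as section 5.8 defines the term, leaves the safety comparison altogether, and more of them come from the water arm.

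**Working it through.** **1. The plan's own figure.** The documents give no AE rate. The only figure tied to the imbalance is the 544 evaluable subjects in SAP 3.3. With difference 0.14, SD 0.58, two-sided 0.05 and 80% power, n per arm = 2 × (1.960 + 0.842)² × 0.58² / 0.14² = 269.4, so 270 per arm and 540 in total. Allowing for 46:54, 540 / (4 × 0.46 × 0.54) = 543.5, so 544. Both figures reproduce.

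**2. Relative retention.** 0.46 × 544 = 250.2 water and 0.54 × 544 = 293.8 control. With equal arms at V3 (an assumption, supported by the balanced V2-V3 drop-out in SAP 6.3), retention under water is 250.2 / 293.8 = 0.852 times that of control.

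**3. Model.** Inputs not in the documents, each shown over a range:
- N, subjects per arm at V3: 300 to 400. N = 340 corresponds to the protocol's upper drop-out figure of 20%, since 544 / 0.8 = 680.
- f, the fraction of the year for which a drop-out is observed: 0, 0.25 or 0.5, the same in both arms.
- r, AE rate per year: constant and equal in both arms, 0.05 to 1.0.

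With drop-out d = 1 - evaluable/N:
- observed time per subject = (1 - d) + d × f
- proportion with at least one AE = (1 - d)(1 - exp(-r)) + d(1 - exp(-r × f))

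Evaluable subjects are treated as observed for the full year.

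**4. One case in full.** N = 340, f = 0.25, r = 0.7. Drop-out is 26.4% water and 13.6% control.
- Observed time: 0.736 + 0.264 × 0.25 = 0.802 years (water); 0.864 + 0.136 × 0.25 = 0.898 years (control). Ratio 0.893.
- Proportion with an AE: 0.736 × 0.5034 + 0.264 × 0.1605 = 41.3% (water); 0.864 × 0.5034 + 0.136 × 0.1605 = 45.7% (control). Ratio 0.904, although the true ratio is 1.

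**5. Range of the crude water/control ratio when the true ratio is 1.**

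| N per arm | Drop-out water / control | f | Time ratio | r = 0.05 | r = 0.3 | r = 1.0 |
|---|---|---|---|---|---|---|
| 300 | 16.6% / 2.1% | 0.25 | 0.889 | 0.890 | 0.894 | 0.904 |
| 300 | 16.6% / 2.1% | 0.5 | 0.927 | 0.928 | 0.932 | 0.945 |
| 340 | 26.4% / 13.6% | 0.25 | 0.893 | 0.894 | 0.898 | 0.909 |
| 340 | 26.4% / 13.6% | 0.5 | 0.931 | 0.932 | 0.937 | 0.949 |
| 400 | 37.4% / 26.6% | 0.25 | 0.898 | 0.899 | 0.903 | 0.915 |
| 400 | 37.4% / 26.6% | 0.5 | 0.937 | 0.938 | 0.943 | 0.954 |

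With f = 0 the ratio is 0.852 in every row. Under this model a person-time rate ratio returns 1.

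**6. Where the distortion shrinks or reverses.** At r = 3 to 5 (N = 340) the crude ratio is 0.94-0.96 with f = 0.25 and 0.98-0.99 with f = 0.5. If all harms occur early and are reported before leaving, the crude ratio is 1 and the person-time ratio misleads instead: at N = 340, 0.898 / 0.802 = 1.12, and 1.11-1.12 over the range of N with f = 0.25.

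**7. Effect of the section 4.1 set.** At N = 340 it would remove about 340 - 250 = 90 water and 340 - 294 = 46 control subjects from the safety comparison.

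**The case against.** The strongest reply is that the SAP says only incidence, so calling the comparison crude is inference from silence. That is fair. But section 5.7.2 treats diabetes incidence as a binary outcome for logistic regression, so a proportion is the natural reading, and nothing in the plan directs otherwise.

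The size rests on undocumented inputs. Any out-of-range laboratory value counts as an AE, so rates may well exceed 1 per year, which pulls the ratio towards 1. The 41.3% vs 45.7% difference is about 1.2 standard errors at 340 per arm. Subjects with a 6-month value only also count as evaluable, so treating all evaluable subjects as fully observed is a simplification. These points limit the size but leave the mechanism intact.

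Person-time is no cure-all. If people leave because they tolerate the water poorly and report nothing, censoring them at last contact still records no event. This objection stands and shapes the fix.

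A reader might also infer two stronger things that the documents do not support:
- **That water subjects leave earlier.** The SAP gives a higher drop-out rate. Section 6.3 refers to preliminary data on completed V6, which suggests that the imbalance was visible by then, but no passage gives timing by arm.
- **That the start of registration itself hides water harms.** The protocol says "Registration of AEs will start with the 1st telephone contact", but the rule is common to both arms and each contact asks back to the previous one, so the first call should cover the time since V3. Only subjects never reached after V3 are missed, and an earlier nominal start would not recover their events.

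Drop-out numbers by arm are already to be reported (sections 5.1.1 and 5.8). They show the imbalance but do not correct the AE comparison.

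**Conclusion.** The concern holds in a limited form. A comparison of AE and SAE incidence among V3 attenders that ignores time observed can understate water-arm events relative to control, because detection depends on staying in contact and more post-V3 drop-out is expected under water. With equal arms at V3, the 46:54 split and equal, constant rates of 0.05 to 1.0 per year, the apparent relative shortfall is roughly 5-15%, and the upper end needs drop-outs to contribute no observed time. It is smaller at high AE rates and nil for early harms reported before leaving. That water harms will be under-counted is therefore conditional, not established.

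The conflict between sections 4.1 and 5.7.3 over the safety population needs no assumptions and should be settled at the same time. This is a worthwhile, low-cost improvement; it does not bear on the primary analysis.

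**What to change.** In SAP 5.7.3:
- Use one safety set, all who attended V3, and amend section 4.1 so that AE and SAE evaluation no longer sits in the set that requires two glucose values.
- Define incidence. Report by arm both the proportion with at least one event and the rate per person-time from V3 to last study contact (or time to first AE censored at last contact), for AEs and SAEs, with total and median follow-up time.
- Report laboratory AEs per attended visit, since they can be found only there.
- State that censoring at withdrawal may be informative, and tabulate by arm the AEs recorded at or before withdrawal.

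**Cost.** SAP wording and an extra column or two. Visit dates are already needed for section 5.4, and the protocol's data-handling section has bookings and follow-up documentation in the study database. If call dates cannot be retrieved, the last attended visit can serve, and that should be stated. No new data collection is needed. An exit interview should not be presumed, because none is described.

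**Downside.** The person-time ratio can overstate water harms if events cluster early, which is why both measures should be shown side by side.
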